6.4.2. Qualitative Interviews

Qualitative interviews for TAU and Care Responders delivered during the pilot window

Qualitative data will include semi-structured interviews at T1 and T2 with service users and parents/carers. Qualitative inquiry with children involved in research is important to inform service design (Martin-Kerry et al., 2019).

Semi-structured interviews exploring experience, acceptability and subsequent wellbeing will be held by the research team at suitable locations (e.g., CAMHS, familiar youth group support setting, or the service user's home or school, depending upon their preference). There will be an option for the young person to attend in person or online through Teams, and they may invite a trusted adult to accompany them if they so wish. Adults will be encouraged to attend interviews alone when possible. Data will be transcribed verbatim by software and then checked by a senior member of the research team. Transcripts will then be anonymised and analysed under the close supervision of SP. SP, GW, FL, KL and ZE will hold regular interpretation meetings with the research workers during the analytic period to offer a space for reflection and to critically assess the reflexivity and transparency of the ongoing analysis.

Qualitative interviews for past-TAU participants and case study participants

Semi-structured interviews exploring experience, satisfaction and subsequent wellbeing will be held by the research team at suitable locations (e.g., CAMHS, familiar youth group support setting, or the service user's home or school, depending upon their preference). There will be an option for the young person to attend in person or online through Teams, and they may invite a trusted adult to accompany them if they so wish. Adults will be encouraged to attend interviews alone when possible. Data will be transcribed verbatim by software and then checked by a senior

member of the research team. Transcripts will then be anonymised and analysed under the close supervision of SP. SP, GW, FL, KL and ZE will hold regular interpretation meetings with the research workers during the analytic period to offer a space for reflection and to critically assess the reflexivity and transparency of the ongoing analysis.

Qualitative interviews with practitioners

Research interviews will also be held with the MHPs and Police Officers working on the MHJRC throughout the research study to collect iterative data on their experiences. Service leads and relevant practitioners (e.g., CAMHS crisis care pathway and emergency triage; GM N=30; Merseyside N=20) will also be interviewed at relevant stages of piloting and evaluation to explore their perspectives on the process and implementation. Again, staff participants will have the option of attending in person at a convenient location (i.e., their place of work/home) or online through Teams.

Informed Assent/Consent for Interviews

As for other stages of the study, informed assent and/or consent will be obtained prior to the start of the qualitative interviews. Participants will be provided with multiple options to confirm and document their informed consent, depending on whether contact with the research team will be face-to-face or via remote means. These will include: 1) signing a hard copy of the consent form during face-to-face meetings with research workers; 2) returning a signed hard copy of the consent form to the research team via standard mail (using a pre-paid return envelope provided by the research team); 3) returning a signed electronic copy of the consent form to the research team via email and 4) providing audio-recorded consent (this will be recorded by research workers using an encrypted recording device and stored separately from any research data collected from study participants).

Following consent, the research workers will conduct semi-structured interviews according to the draft topic guides included with this NHS ethics/health research authority (HRA) application. The topic guides used to inform the qualitative interviews will be a living document, updated according to emerging findings from earlier interviews, new published literature in this area and feedback from our ongoing stakeholder consultations.

Interviews may take up to 90 minutes, depending upon how much or little participants wish to say, and will be recorded using encrypted recording devices. Participants will be asked if they would like to receive copies of their interview transcripts and a summary of the emerging findings of the study, for the purposes of ensuring accuracy and contribute to 'member checking' procedures to ensure the trustworthiness of the study findings.

6.4.3. Health Economic Evaluation

The MHJRC is a complex intervention that will have impacts on multiple sectors. Cost consequence analysis (CCA) has been recommended for complex interventions that have multiple effects and for public health interventions which have an array of health and non-health benefits that are difficult to measure in a common unit (NICE, 2013a; Shah et al., 2012). Unlike cost-effectiveness and cost-benefit analyses, CCA does not require the research team to impose a specific disciplinary or professional perspective on the analysis, and instead allows decision makers to examine the impact of different perspectives. We will use a micro costing approach. This methodology uses detailed data on resource utilisation from NHS digital and unit cost data (available from: https://www.pssru.ac.uk/project-pages/unit-costs/) to generate precise estimates of economic costs. By clearly outlining all the costs occurred, other trusts can identify potential differences in costs related to roll-out. Data collection will largely be from PCFT and GMP intranet data and routine outcome measures, with additional demographic and impact questions (e.g., days missed from school/work) added to data collection points within the realist evaluation. As this is an acute/crisis intervention, a marker of success is the prevention of admission to hospital and increase in recovery focused measures at follow up. Co-applicant GW is involved in the REEM project (NIHR 135102), which seeks to develop methods for realist economic evaluations. He will be able to share any relevant findings from the REEM project as they emerge, hence potentially informing the conduct of workstream 3.

CCA will be informed by workstream 1 and, where possible, will test and refine theories in relation to economic evaluation, service resilience, and other key factors of importance identified. The analysis is likely to employ cost data on health service utilisation from NHS records of emergency admissions, over-night stays in hospital awaiting assessment, and section 136s. The evaluation will collect data on and assess:

- 1. Costs of delivering the MHJRC, offering learning on police, emergency department, and wider NHS spending and potential savings.
- 2. Changes in cost-of-service usage compared to a non-joint response.
- 3. Average change in cost per person between the MHJRC and care as usual.
- 4. Time off work/school. NHS costs will be obtained from questionnaires to caregivers and young people at T1 and T2.
- 5. Time spent attending to emergencies compared to indirect work (note keeping, updating records), systemic liaison (e.g., safeguarding), and other duties, compared with idle time.
- 6. The cost implications of journey times in boroughs that are more rural and/or that present additional obstacles for the vehicle (e.g., busy one-way systems in intensely urban areas, rural roads with poor road surface conditions, the impact of climate at specific time points, etc.).

A micro costing approach will enable the analysis of detailed data on resource utilisation from NHS digital and unit cost data (available from: https://www.pssru.ac.uk/project-pages/unit-costs/) to generate precise estimates of economic costs. By clearly outlining all the costs occurred, other trusts can identify potential differences in costs related to roll-out. We will include the location of callouts, time to drive to and from each location, and qualitatively explore the perceived impact of location upon the service from the perspective of the attending first responders as a core part of workstream 3.

6.5 Realist Data Analysis

Initially, quantitative data will be entered into SPSS. Depending upon the completion of data sets and whether we achieve our recruitment targets, we will either conduct a descriptive analysis or regression analyses. Advice will be sought from HB in statistics, and the statisticians in the MASH Centre at Lancaster University. NVIVO will store and categorise anonymised transcribed data. Data analysis will be concurrent with data collection, in line with realist interviewing conventions (Brönnimann, 2022). Data analysis will help us understand and explain why the MHJRC works in the way it does for young people and families when called to a mental health crisis, in which contexts and to what extent. This will allow us to develop an in-depth, realist understanding and explanation of the impacts observed. Each new element of relevant data will be used to refine aspects of the programme theory. As it is refined, data sources will be re-scrutinised to search for data relevant to the revised programme theory that may have been missed initially. Transcripts will be uploaded to NVivo. Relevant sections of transcripts that have been interpreted as related to contexts, mechanisms and/or their relationships to outcomes will also inform our analysis. This coding will be both inductive (codes created to categorise data identified through the analysis process) and deductive (codes created in advance of data extraction and analysis as informed by the initial programme theory, which will also hold in mind the results of the NIHR128359 (Evans et al., 2023) review).

Relevant data (qualitative and quantitative) will initially be analysed into conceptual themes. We will then use the realist logic of analysis (Brönnimann et al., 2022; Pawson & Tilley, 1997; Pearson et al., 2015; Ritchie & Lewis, 2003) to develop context-mechanism-outcome-configurations (CMOCs) that bring together the different sources of data to provide causal explanations for outcomes of importance with our programme theory. In addition, we will apply a range of reasoning processes associated with realist analysis (Pawson, 2013) to these data, such as juxtaposing data, unpicking conflicting data, and consolidating data, to explain why differences may arise across settings, and how and why identified outcomes have occurred (or not). Our ongoing application of a realist logic of analysis will be guided by a series of questions that members of the team have used in other realist projects:

1. Is this a piece of data that is relevant to programme theory development?

- 2. If so, do its contents provide data that may be interpreted as functioning as context, mechanism, or outcome?
- 3. For data that has been interpreted as functioning as context, mechanism or outcome, which CMOC does it belong to?
- 4. Are there further data to inform this particular CMOC contained within this source or other sources? If so, which other sources?
- 5. How does this particular CMOC relate to others that have already been developed?
- 6. How does this particular CMOC relate to the programme theory?
- 7. In light of this particular CMOC and any supporting data, does the programme theory need to be changed?

We will then use this in-depth understanding and explanation as a starting point of our discussions with the stakeholder groups to refine the final theory.

To ensure active surveillance of harms, the research workers will also actively check for the occurrence of specific AEs during the follow-up period. Participants will be offered flexibility regarding length of follow-up assessment meetings, including the option of having regular breaks and multiple, shorter testing sessions. To reduce the likelihood of missing data, a member of the research team will be able to make multiple attempts to contact participants to engage with aspects of the study up until the time a participant withdraws. Data can be gathered in person or over the phone, Teams, or post. Spurious data will be discussed within the research team, who will decide upon an appropriate response (i.e., deletion, checking, repeated data collection).

6.6 Health Economic Data Analysis

We will perform a cost-consequence analysis of the MHJRC Service as a whole, as well as considering distributional impacts if data allows by age group, gender, sexual orientation, and ethnicity. We will provide, where appropriate, monetarised valuation of the effects of the programme and detail of who experiences them (younger person, young person's family, health service, police services). Heath and care utilisation can also be assigned a monetary value by applying NHS Reference Costs and the PSSRU unit costs. Health and wellbeing outcomes can be monetarised if appropriate. These can include calculating healthy life expectancies and disability free life years (NICE, 2013a; Shah et al., 2012).

Consequences will focus on the health and well-being impacts of the programme as well as impacts on the health service, including wait times for CAMHS services, attendance at A&E for mental health emergencies, police service call outs, to give a few examples, but this list is not exhaustive. Data for the benefits will come from the quantitative surveys in workstream two. We will supplement this data with data on health outcomes such as A&E attendance and waiting times from NHS digital and

data on contacts with the police using police data. We will compare these to the costs of implementing the programme, which will be obtained from The Greater Manchester Health & Social Care Partnership (GMHSCP) and PCFT. This will include considering costs around waiting times between call outs (e.g., costs for staff involved during the whole shift). Costs and consequences will be compared to the baseline scenario of service provision before the introduction of the MHJRC.

We will consider the short-term cost and consequences of the MHJRC using the estimated ex-poste effects from data collected in the quantitative surveys through workstream two. Additional consequences on outcomes related to changes in service usage and contact with the police using data from NHS digital and the police will be obtained by estimating a quasi-experimental model such as difference-indifference or interrupted time series which Co-I HB has extensive experience with (Brown et al., 2022; Thomson et al., 2020). Ex-ante longer-term costs and consequences to young people and their families, health services, and police will be estimated using evidence from the review of the literature from workstream one. We will explore different time horizons given what data is available from the literature and discussions with stakeholders and the public. If data allows, we will also explore feasibility of roll out in less urban areas by thinking about longer drive times and greater waiting times between call outs. Discount rates of 3.5% will be used, as per guidelines (NICE, 2017).

The analysis will be conducted following well-established guidelines (HM Treasury, 2018; Hunter & Shearer, 2014). Missing data will be imputed. Subgroup analysis (distributional cost consequence analysis) will be conducted on samples large enough to identify any effects. In line with recommendations, uncertainty will be incorporated using a combination of scenario based deterministic sensitivity analysis, threshold analysis, and/or probabilistic sensitivity analysis (NICE, 2013b). All parameter estimates will include 95% confidence (or, where appropriate credible intervals), and these will be calculated by applying bootstrapping techniques. We will avoid making a summary assessment of effectiveness and instead enable decision makers to form an overall judgement based on the relative weights they apply to the different consequences. Costs and effects will be disaggregated to allow decision makers to assess the trade-off between costs and effects for each dimension compared to a non-joint response. We will work with local partners to accurately audit the need and associated costs the MHJRC could address, in terms of the numbers of referrals, call outs, and admissions to A&E/s136s. Following vetting and with permission and support from Greater Manchester Police, the health economist team will review police records for data relating to the following factors:

- · Data on call outs to mental health crisis for under 18s
- Care plans developed by police for young people due to mental health
- Outcome data on responses to mental health crisis
- Any data on complexity of cases
- Data on officer training in mental health

[figure not shown]
- Costs of the various call outs/responses/outcomes (e.g., hours waiting in A&E)
- Data on co-responses or joint responses with NHS mental health/ambulance/social services - comparing outcomes between police only and joint responses
- Distances travelled to mental health crisis call outs
- The time call outs and responses take
- Locations/settings of call outs (home, school, out of home placements, inpatient wards, etc.)
- Data on how mental health presentations are recorded
- Liaison between services by officers after a call out (e.g., NHS, social services, safeguarding, etc.).

6.7 Keeping in touch calls.

To promote retention in the study, the research workers will contact research participants a few days before each appointment to confirm details, and then again two weeks prior to T2. These brief telephone calls will be an opportunity for the research workers to remind participants (usually the parent/caregiver bringing the young person to the appointment) of upcoming research engagement and to resolve pragmatic barriers that may delay or hinder the participant's timely engagement in the follow-ups (e.g., ensuring that participant contact details and preference for face-to-face or remote meetings are up to date).

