[name] (CI) was responsible for the drafting of the protocol on the basis of the Detailed Project Plan of the grant application submitted to NIHR and reviewed

through two competitive rounds by committee. [name] and [name] have advised specifically on PPIE matters and have been directly involved in the development of this project over the last two years.

viii. Key words

Brief intervention; first response; child/adolescent mental health

ix. Study flow chart

1. Background and rationale

Challenge: Children and young people are experiencing increasing challenges to their mental health, with services "constantly firefighting" to meet demand (Health and Social Care Committee, 2022). Pathways to mental health care for young people are under-researched (MacDonald et al., 2018) and poorly understood. In February 2023, it was identified the NHS is not reaching targets to increase access and reduce waiting times for young people's mental health services (Department for Health and Social Care, 2023). Data collected by Greater Manchester Police (GMP) shows youth mental health care plans developed by police officers attending to 999 calls have increased by 14.2% between 2021 and 2022. Police officers often feel ill-equipped to

provide mental health support, especially to children and young people experiencing a mental health crisis (Jackson et al., 2019)

Potential solution: Our evaluation would provide the necessary evidence to establish a high-performance intervention model across England through a robust evaluation of the pilot implementation of a MHJRC. In 2022, GMP and Pennine Care NHS Foundation Trust (PCFT) piloted a MHJRC with adults experiencing mental health crises across five Greater Manchester boroughs. The MHJRC involves a police officer and mental health practitioner attending collaboratively to people in crisis who have made a 999 call: combining the response speed of the police and mental health expertise of the practitioner. The MHJRC for adults demonstrated police officers and mental health professionals can collaborate effectively to support people in crisis (Blyth, 2022).

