police and CAMHS. The campaign aims to 'strengthen legislation, guidance and training around policing within a mental health crisis'. If funded, we will aim to collaborate with *Hear Me Speak* and *Beyond* to amplify dissemination activities and provide evidence from our study to their campaigns and legislation development in the near future.

Young people's mental health difficulties have increased in scale and complexity in recent years, with COVID related school closures and social media-based bullying cited as recent aggravating factors (Newlove-Delgado et al., 2022). There are increases in the need for emergency mental health care, but little research has been conducted with young people and their families to explore what this emergency support would look like and how it could be operationalised. According to GMP records, the number of \$136's for young people under 18-years-old rose from 77 between 01/04/20-31/03/21 to 115 between 01/04/21-31/03/22. However, despite a clear need for supportive emergency care for young people in mental health crisis, emergency care is extremely limited and generally experienced as unsupportive. A recent survey (Buchanan et al., 2022) found:

- 54% of respondents to a satisfaction questionnaire reported child and adolescent mental health services (CAMHS) for emergency care were 'poor' or 'awful'.
- 40% reported emergency care had worsened in 'service quality' over the last 3 years.
- 64% of respondents reported no service availability after 17:00.
- Two thirds of respondents reported waiting times of over 24 hours for a hospital bed, with free text comments indicating some patients had waited 5 days.

CAMHS often operate during typical working hours (8am-6pm), which has meant that it is difficult to integrate paediatric emergency services into existing CAMHS structures. This lack of service integration has a significant impact upon service quality and child safety. Epidemiologic studies in relation to care pathways of mental health and self-harm emergencies attended by first responders are scarce, even though between 10% (NHS Digital, 2015) and 40% (Data Analytics Lab, 2020) of calls to emergency services relate to a mental health crisis. Therefore, we have a limited understanding of who helps people outside of typical working hours when they are most in need, especially for children.

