The pilot and evaluation will be based in Greater Manchester, with participant identification, recruitment and treatment for participants of the pilot Care Responders car taking place through the new MHUT model, the police triage unit, and any other triage centre in Greater Manchester responding to 111/999 calls. MHUT links with Greater Manchester Police (GMP), Greater Manchester Mental Health NHS Foundation Trust (GMMH), Pennine Care NHS Foundation Trust (PCFT), and Manchester University NHS Foundation Trust (MFT) to coordinate emergency care and crisis care pathways. We are already liaising with the Strategic Lead for Mental Health Crisis and Liaison for Greater Manchester, senior members of GMP, and the Greater Manchester integrated care system (ICS) to ensure outputs are useable, feasible and supported through to implementation with the support of the newly formed MHUT, which is currently being set up, to work alongside existing triage centres with a view to MHUT accepting all 999/111 calls in time.

Nested Case Study Design

We have received additional funding from the NIHR to include a nested case study for a non-intervention data gathering case study site in Merseyside with Mersey Care NHS Foundation Trust. This nested case study employs a qualitative approach, aligned with Priya's (2021) assertion that case study methodology enables an indepth exploration of complex phenomena within real-life contexts. The focus is upon CAMHS crisis care in Merseyside, allowing for nuanced insights into personal experiences and the contextual factors influencing the effectiveness of mental health crisis interventions in this additional setting. This design incorporates flexibility to adapt to specific elements critical to the effectiveness of the model in Merseyside, with findings transferable to Greater Manchester (GM).

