6.4.1. Measures

The Strengths and Difficulties Questionnaire (SDQ; routinely employed screening and outcome measure in CAMHS) will be used at T1 and T2. The SDQ is a brief behavioural screening questionnaire for 2-17-year-olds. This single-informant measure assesses child-wellbeing and is used by clinicians at the point of referral and exit in CAMHS. Our choice of other questionnaires will be finalised by the programme theory but will likely include:

T1

Analysis of routine data sets held by GMP and PCFT (e.g. care plans, A&E admissions, acute care pathway referrals) in relation to each contact who has engagement with the MHJRC, with an additional EDI lens to evaluate whether the routine data points capture information about the context of the individual that could inform greater cultural sensitivity and accessibility. Experience of Service Questionnaire (ESQ) Child Self-report for 9–11-year-olds, ESQ Child Self-report for 12-18-year-olds, ESQ Parent/carer report

Therapeutic Experience Scale with young people, parents/carers, and staff (STAR-P and STAR-C)

KidCOPE scale 7-12, KidCOPE scale 13-18

Child and Youth Resilience Measure-Revised (CYRM, 5-9-years-old; CYRM, 10-23years-old)

Parental Stress Scale (PSS)

Session Rating Scale (SRS)

Short Mood and Feelings Questionnaire (sMFQ)

EQ-5D-Y-3L child-friendly EQ-5D version (EQ-5D-Y)

MHJRC PCFT staff will keep tabulated records of how time is spent. The study team will collaborate with members of the adult MHJRC team to develop a 'heat map' of youth and adult need/call outs across the service footprint, considering location, frequency, and key timings.

T2

Repeat ESQ, KidCOPE, CYRM-R, PSS.

These measures will address the research questions by gathering data on the impact of the MHJRC on wellbeing, service experience, therapeutic nature of relationships,

coping ability over time, and stress. This data will be enriched through the collection and analysis of qualitative data from the interviews.

!			
 			
1			

Time point / Participant group	In person/video call T1 (within 12 weeks of engagement with MHJRC/TAU)	In person/ video call T2 (3-month follow-up)	In person/ video call T2 (6- month follow-up)	Qualtrics Survey T1 Route 1: within 12 weeks of engagement with MHJRC/TAU Route 2: Within two years	Qualtrics Survey T2 (Only if Route 1: T1 was within 12 weeks of engagement with MHJRC/TAU)

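### Section 6.6 compares costs and consequences with provision before the car, but 6.4.3 and 6.6 itself also compare with non-joint response or usual care; one comparator is needed, with MHUT separated from the car

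*Protocol*

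**What the plan says.** The protocol names the economic comparator in several places.

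- Section 6.6, after listing the sources for benefits and programme costs: "Costs and consequences will be compared to the baseline scenario of service provision before the introduction of the MHJRC".
- Section 6.4.3, item 2: "Changes in cost-of-service usage compared to a non-joint response".
- Section 6.4.3, item 3: "Average change in cost per person between the MHJRC and care as usual".
- Section 6.6, later: the trade-off on each dimension is again judged against a non-joint response.

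Section 6.6 takes the benefits data from the workstream 2 surveys. Section 6.4 describes these as 100 users of the mental health joint response car (MHJRC) and 100 users of traditional services recruited through MHUT. Both groups are surveyed within 12 weeks of contact and at six months.

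For changes in service use and police contact, Section 6.6 plans "estimating a quasi-experimental model such as difference-indifference or interrupted time series", using NHS Digital and police data. The model is offered as an example and no control is named.

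Three pieces of context matter.

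- Section 1 reports that police youth mental health care plans "have increased by 14.2% between 2021 and 2022", and that under-18 Section 136 detentions "rose from 77 between 01/04/20-31/03/21 to 115 between 01/04/21-31/03/22".
- Section 1 expected MHUT to launch towards the end of 2023. Section 4 describes it as still being set up, "with a view to MHUT accepting all 999/111 calls in time". The project summary starts the pilot in August 2024.
- Section 6.4.1 words the T1 analysis of routine Greater Manchester Police (GMP) and Pennine Care (PCFT) data "in relation to each contact who has engagement with the MHJRC".

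**The concern.** Provision before the car and non-joint response are different counterfactuals. They give different incremental costs and different counts of avoided events, and nothing says which one governs.

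The difference matters because the system was not standing still. Demand was rising on the protocol's own evidence, and a new triage model was being introduced around the start of the pilot. A contrast with the period before the car is therefore also, in part, a contrast with the period before or early in MHUT, at a different level of demand. The results are meant to inform wider adoption, so decision makers need costs and consequences that belong to the car.

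**Working it through.** The protocol gives no precision, power or effect figure for the economic comparison, so there is none to reproduce. The check has two parts: a reading of the comparator wording against the data sources, and the size of the time trend.

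**1. Comparator against data source**

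| Quantity | Stated source | Data from before the car? |
|---|---|---|
| Survey benefits | Workstream 2 surveys, MHJRC and traditional services (6.4, 6.6) | No survey wave |
| Routine service use and police contact | NHS Digital and police data (6.6) | Needed for difference-in-difference or interrupted time series |
| Programme cost | GM Health & Social Care Partnership and PCFT (6.6) | Not covered by the quasi-experimental clause |

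Pathway Two admits usual care received up to two years earlier, so some respondents may predate the car. They are self-selected, and the assessment table in 6.4.1 offers an online T2 only where T1 fell within 12 weeks of contact. They do not replace a survey wave before the car.

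**2. Size of the trend**

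Inputs from Section 1: care plans +14.2% in one year; under-18 Section 136 detentions 77, then 115.

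- Section 136 ratio: 115/77 = 1.494, or +49.4%. Treating the counts as Poisson, the standard error of the log ratio is √(1/77 + 1/115) = 0.147, giving a 95% interval of 1.12 to 1.99.
- Care plans: underlying counts are not given, so no interval can be formed.

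For an unadjusted before-after contrast, apparent change = (1 − true reduction) × (1 + growth) − 1. The gap between periods is not stated; one year is assumed.

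| True effect of the car | Growth 14.2% | Growth 49.4% |
|---|---|---|
| None | +14.2% | +49.4% |
| 20% reduction | 0.80 × 1.142 − 1 = −8.6% | 0.80 × 1.494 − 1 = +19.5% |

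The true reduction that one year's growth would exactly cancel is 1 − 1/1.142 = 12.4%, or 1 − 77/115 = 33.0%. Over two years at 14.2% a year, growth is 1.142² − 1 = 30.4%. The 49.4% is best read as an upper illustration, since its first year, from April 2020, may have been depressed by the pandemic.

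**3. MHUT**

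The documents give no MHUT effect, so a range is assumed. If MHUT alone cut events by 10% to 30% and the car did nothing, a before-after contrast with no trend would show −10% to −30%, all of it attributed to the car. With 14.2% growth as well, it would show 0.90 × 1.142 − 1 = +2.8% to 0.70 × 1.142 − 1 = −20.1%. The two distortions run in opposite directions and could partly cancel, so the net sign cannot be known in advance.

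**4. What the quasi-experimental model removes**

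An interrupted time series without a control models the prior trend but cannot separate two changes introduced at about the same time. Difference-in-difference can do so only if the control also moves to MHUT. Neither is stated to cover programme costs or survey outcomes.

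**The case against.** The strongest reply is that the first sentence is loose wording. Both named quasi-experimental models need a pre-period, so the baseline scenario may simply be that pre-period, and the choice of model and control can be left to an analysis plan that is not shown here. This stands in part: for routine outcomes, the protocol does not commit to an unadjusted contrast. But the sentence is written for costs and consequences as a whole, and the model is not. A contradiction in the comparator is on the face of the protocol and is not merely deferred detail.

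Four stronger readings are tempting and are not supported.

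- A reader might infer that rising demand would be credited to the car. For event counts it works the other way: more events after introduction hide a benefit or look like harm. Only a favourable MHUT effect would be credited.
- A reader might take 14% to 30% (one to two years at 14.2%) as the bias of the planned analysis. It applies only to an unadjusted contrast in event counts, and does not carry over to cost per person.
- A reader might infer from the T1 wording in 6.4.1 that admissions of usual-care participants at other Trusts are not captured. Sections 6.4.3 and 6.6 also draw on NHS records, NHS Digital, questionnaires to families and police records that compare police-only with joint responses. None of these is limited to car contacts.
- A reader might see a clean split between 6.6 and 6.4.3. Section 6.6 uses both comparators, and 6.4.3 does not say that usual care is concurrent.

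MHUT is also less of a problem for the surveys. Usual-care respondents are to be recruited through MHUT, and car participants come through MHUT and other triage units, so both groups can sit under the new model.

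**Conclusion.** The concern holds in a limited form. The protocol states its economic comparator inconsistently, and one of the stated comparators does not fit the surveys named as its source of benefits. If the before-after comparison were carried out plainly, one year of the protocol's own reported growth would cancel a true reduction of 12.4% (care-plan trend) or 33.0% (Section 136 trend), and any favourable MHUT effect would be counted as the car's.

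These sizes assume a one-year gap, continued growth at the reported rate and no adjustment. They show why the choice matters and do not estimate the bias of the final analysis. For routine outcomes, the remaining weakness is that the protocol permits an interrupted time series without a control, which would deal with the prior trend but not with MHUT.

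**What to change.** Replace the before-introduction sentence in 6.6, and align 6.4.3 with it, along these lines:

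1. The primary comparator for costs and consequences is non-joint response (care as usual) in the same calendar period.
2. For routine service-use and police-contact outcomes, use difference-in-difference or a controlled interrupted time series. The control must also be exposed to MHUT, for example Greater Manchester boroughs not served by the car, if such exist; the car's coverage needs to be confirmed first.
3. Data from before the car serve only as the baseline of that model. A simple before-after contrast is kept as a sensitivity analysis.
4. The same routine outcome fields are drawn over the same footprint for both groups, with the T1 wording in 6.4.1 amended to match.

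The cost is wording plus a somewhat wider cut of police and NHS data already being requested, with no new participants. There is one downside: same-period non-joint responses may differ from car responses because triage decides who gets the car. The protocol should acknowledge that selection when it names the comparator.
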